#### Abstract

#### Background:

Adequate pain control after thoracoscopic surgery for lung resections is important to improve postoperative mobilization and recovery, to prevent pulmonary complications. Despite increased use of thoracoscopic surgery, clinically relevant pain is still present in 38% of the patients. Although frequently performed, guidelines report no consensus on the preferred analgesic technique during thoracoscopic surgery. Thoracic epidural analgesia is currently the standard of care due to its clear analgesic effect, however, related adverse events have triggered a growing interest in alternative locoregional analgesic techniques, such as paravertebral block or intercostal nerve block. Until now, evidence to change the standard of care is scarce. The OPtriAL evaluates whether a continuous paravertebral block or a single-shot intercostal nerve block are non-inferior to thoracic epidural analgesia regarding pain and superior regarding quality of recovery.

#### Methods:

We established a statistical analysis plan for transparent reporting of data analysis regarding the OPtriAL study. For this study, patients undergoing thoracoscopic anatomical lung resection are randomized into one of three arms: thoracic epidural analgesia, continuous paravertebral block or single-shot intercostal nerve block. Co-primary outcomes are: a) proportion of pain scores  $\geq$  4 as assessed with the numerical rating scale during postoperative day 0 until postoperative day 2 and b) quality of recovery, measured with the quality of recovery-15 questionnaire on postoperative days 1 and 2. In order to be non-inferior, the upper margin of the 98.65% one-sided confidence interval of the difference in mean proportions of pain scores  $\geq$  4 between the continuous paravertebral block and single-shot intercostal nerve block, both separately compared with the thoracic epidural analgesia, may not exceed 17.5% (predefined non-inferiority margin). Intention-to-treat and perprotocol analyses should both indicate non-inferiority to implement the intervention techniques as relevant alternatives to thoracic epidural analgesia. We expect a counterbalancing gain in quality of

recovery, which will be tested for superiority. Secondary outcomes such as length of stay, complications and patient mobility will also be tested for superiority.

## Discussion:

The results of the OPtriAL will provide level 1b evidence to optimize postoperative pain management and perioperative care for thoracoscopic anatomical lung resections.

Trial registration: The trial is registered at the Netherlands Trial Register (NTR) on February 1st, 2021 (NL9243). The NTR is no longer available since June 24th, 2022 and therefore a revised protocol (Version 3, date May 6th, 2022) has been registered at ClinicalTrials.gov on August 5th, 2022 (NCT05491239).

SAP version: Version 1, dd 11-10-2023

Protocol: This statistical analysis plan has been written based on the information contained in the published study protocol version 3 (1).

Keywords: Statistics, Clinical trial, Pain, VATS, Lung surgery

#### **Background and rationale**

Considerable improvements have been made by the implementation of thoracoscopic surgery for anatomical lung resections compared to open surgery in terms of less postoperative pain, shorter length of stay (LOS) and faster recovery (2), however, acute postoperative pain is still present in a large proportion of patients (3). Adequate pain control is important to improve postoperative mobilization, recovery and patient satisfaction, and prevent pulmonary complications. Whereas guidelines lack consensus on the preferred analgesic technique, thoracic epidural analgesia (TEA) is considered the standard of care due to its clear analgesic effect. However, associated adverse events have triggered a growing interest in alternative loco-regional analgesic techniques. Recent PROSPECT (4) and European guidelines (5) recommend the use of loco-regional analgesic techniques, including paravertebral block (PVB), intercostal nerve block (ICNB) and erector spinae block. Until now, evidence to change the standard of care is scarce and a recent systematic review reports great interstudy heterogeneity (6) and the need of more rigorous clinical evidence from a randomized clinical trial. The OPtriAL is a three-arm multicentre pragmatic randomized trial comparing continuous PVB, single-shot ICNB and TEA regarding pain and quality of recovery (QoR) in patients undergoing thoracoscopic anatomical lung resection. The objective of the OPtriAL is to provide high quality level 1b evidence to be implemented in enhanced recovery after thoracic surgery (ERATS) protocols. We hypothesize that continuous PVB or single-shot ICNB is non-inferior to TEA regarding postoperative pain but superior regarding QoR. This may imply faster postoperative mobilization, reduced morbidity, and shorter hospitalization. Loco-regional techniques may therefore reduce health care costs and improve patient satisfaction.

#### Summary of the study protocol

The OPtriAL (Optimal postoperative Pain management After thoracoscopic Lung resection) is a threearm multicentre pragmatic randomized controlled trial comparing TEA, continuous PVB and single-

shot ICNB in adult patients undergoing thoracoscopic anatomical lung resection. The study comprises two co-primary outcomes with different designs: a non-inferiority design for the outcome 'pain' and a concomitant superiority design for the outcome 'quality of recovery'.

Adult patients (>18 years) referred for thoracoscopic anatomic lung resection (segmentectomy, (bi)lobectomy and pneumonectomy for either benign or malignant disease) are eligible for the trial. We exclude patients with a contraindication for one of the analgesic techniques, chronic use of opioids, a high probability of conversion to thoracotomy or in case of insufficient Dutch proficiency. Written informed consent is obtained from each participating patient before randomisation. Patients are randomized in a 1:1:1 ratio for one of the three analgesic techniques by a computerized database (Research Manager) with an unchangeable computer-generated number. Randomization is done in random block sizes of 6, 9 and 12. As anaesthesia and surgical protocols may slightly differ between hospitals, randomization is stratified by treatment centre. Blinding is unfeasible due to clear visible differences of the analgesic techniques and would potentially compromise the safety of the patient (analgesic catheter, indwelling urinary catheter, mobility with or without prerequisites).

The first co-primary outcome relates to pain and the second to QoR. Pain is measured with the numerical rating scale (NRS 0-10; 0=no pain, 10=worst imaginable pain). A NRS score <4 indicates acceptable pain and ≥4 indicates unacceptable pain as it implies the clinical need for additional analgesia. Therefore, our primary outcome 'pain' for non-inferiority is expressed as the proportion of postoperative NRS scores in rest ≥4, defined as the number of NRS ≥4 measurements divided by the total number of NRS measurements obtained from postoperative day (POD) 0 until POD 2. Each patient has a maximum of 8 measurements: at the recovery room, the evening of the day of the operation, and in the morning, afternoon and evening of POD 1 and 2. Superiority of the second coprimary outcome 'QoR' is measured with the QoR-15 questionnaire (lowest score of 0 and highest score of 150) at POD 1 and POD 2.

Non-inferiority for pain is obtained only if the upper limit of the 98.65% one-sided confidence interval (CI) of the differences of mean proportion of NRS  $\geq$ 4 between the PVB versus TEA and ICNB versus TEA remains below the predetermined absolute margin of 17.5% in the intention-to-treat (ITT) analysis as well as in the per-protocol (PP) analysis. This non-inferiority margin is based on data from a previous pilot study, in which the proportion of pain scores  $\geq$  4 in a group of patients receiving TEA was 17.57% (SD 19.57) and in patients receiving continuous locoregional analgesia 21.21% (SD 23.33). Since the baseline of 17.57% of moments of pain in the control group is low, we accept an absolute margin of 17.5% from a clinical point of view. This margin of non-inferiority, accepting more moments of pain in the intervention techniques as compared to the control group, is justifiable in combination with superiority regarding QoR. Superiority regarding QoR is defined as a significantly higher mean score during POD 1 and POD 2 (p < 0.027) in the ITT analysis. Taking the mean QoR score during POD 1 and POD 2 is a simplifying improvement of the original superiority definition in the published study protocol (1) without affecting the sample size calculation.

Secondary outcomes are: 1) pain scores during rest and mobilization at the recovery room, in the evening of the day of operation, and in the morning, afternoon and evening on POD 1 until POD 3, and at 2-3 weeks follow-up; 2) proportion of NRS scores ≥4 during mobilization during POD 0 until 2; 3) QoR-15 at POD 0, POD 3 and 2-3 weeks follow-up; 4) cumulative use of opioids and analgesics at POD 0 until 3 and the plain use of opioids at 2-3 weeks follow-up; 5) postoperative complications until POD 30; 6) hospitalisation; 7) patient satisfaction at POD 0 until 3; 8) time to removal of the chest tube; 9) time of an indwelling urinary catheter; 10) degree of mobility at POD 0 until 3 and 11) cost-effectiveness analysis (separate analysis).

The sample size calculation resulted in 450 patients in total (150 for each randomization group) to demonstrate non-inferiority regarding proportion of NRS measurements ≥4 (power 99%, one-sided Type 1 error of 0.0135) as well as superiority regarding QoR (power 90%, two-sided Type 1-error of 0.027), taking into account an assumed 12.6% drop-out for conversions to thoracotomy (in the Netherlands, data from the Dutch Lung Cancer Audit from 2017) and controlling for the family-wise

error rate associated with the comparison of the two experimental groups (PVB and ICNB) with the same control group TEA (1).

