#### Analysis

For appointing non-inferiority, both the ITT and PP will be performed and both should attain to the predetermined non-inferiority margin (the one-sided 98.65% CI upper bound of the difference in proportions not exceeding 17.5%). For superiority (p<0.027), the ITT analysis will be considered as the primary analysis and the PP as a supportive analysis. For secondary outcome measures, solely the ITT analysis will be performed.

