#### Quality of recovery

QoR will be measured with the QoR-15 questionnaire at POD 1 and 2, and reported as the mean of these two values (Figure 2C). This outcome will be expressed as a discrete variable (minimum 0, maximum 150). Comparisons to test superiority will be made for the TEA versus PVB group and the TEA versus ICNB group. Superiority in terms of QoR is defined as a statistically significant higher mean score (p<0.027).

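### The fixed 0.027 / 98.65% levels are valid, but a step-down form would target the same family-wise error with more power for the second technique

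*SAP*

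**What the plan says.** The sample size paragraph in Summary of the study protocol gives the levels as "power 99%, one-sided Type 1 error of 0.0135" for pain and "superiority regarding QoR (power 90%, two-sided Type 1-error of 0.027" for QoR. It says they control the family-wise "error rate associated with the comparison of the two experimental groups (PVB and ICNB) with the same control group TEA".

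The decision rules repeat these levels as fixed thresholds:
- **Pain.** The Analysis section requires "the one-sided 98.65% CI upper bound of the difference in proportions not exceeding 17.5"%, in both the ITT and the PP analysis. The Methods part of the abstract, Summary of the study protocol and the Pain subsection use the same limit. Appendix A shows it as 98.6%.
- **QoR.** Summary of the study protocol asks for a "significantly higher mean score during POD 1 and POD 2 (p < 0.027) in the ITT analysis". The Quality of recovery subsection asks for a "statistically significant higher mean score (p<0.027").

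The SAP does not order the two techniques, and no rule changes the level for one technique after the other has succeeded. It names neither the correction method nor the overall error level. It states power per comparison and gives no figure for both techniques succeeding.

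**The concern.** A single-step correction guards against two false claims at once. Once one technique has met its claim, at most one null hypothesis is left that could still be rejected falsely. The remaining technique can then be tested at the full family-wise level without taking the family-wise error above its target. Under the present rule, a second technique with a QoR p-value between 0.027 and 0.05, or whose pain limit meets 17.5% at 97.5% but not at 98.65%, is denied its claim although that error would still be controlled.

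This matters because PVB and ICNB are separate options for practice, each with its own comparison against TEA. The SAP also justifies the wide pain margin by a gain in QoR, so a technique that misses on QoR loses the support for its pain claim as well.

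**Working it through.** **Inputs from the SAP**
- Levels: 0.027 two-sided for QoR and 0.0135 one-sided for pain. QoR power is 90% per comparison.
- Allocation: "Patients are randomized in a 1:1:1 ratio for one of the three analgesic techniques". With equal variances, the two contrasts against TEA correlate 0.5.
- Size: "The sample size calculation resulted in 450 patients in total (150 for each randomization group"), with 12.6% drop-out, which leaves 150 × (1 − 0.126) ≈ 131 per arm.
- Pain: TEA 17.57% (SD 19.57), locoregional 21.21% (SD 23.33), margin 17.5%.

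**Assumptions**
- Both techniques have the design effect.
- The PP analysis agrees with the ITT analysis.
- The normal approximation holds.
- The correlation between pain and QoR is 0 to 0.5 (not given in the SAP).

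**1. Reproducing the SAP's levels.** Take two contrasts with correlation 0.5 and find c such that P(max|Z| > c) = 0.05. This gives c = 2.212, a two-sided p of 0.02696, which rounds to 0.027. An overall one-sided level of 0.025 gives the same c and p = 0.01348, which rounds to 0.0135. Bonferroni gives 0.0250 and Šidák 0.0253, so neither fits. Single-step Dunnett at 0.05 two-sided / 0.025 one-sided is therefore a firm inference.

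**2. QoR, both techniques succeed.** The QoR effect and SD are not in the SAP and are not needed. Power of 90% at 0.027 fixes the mean of each test statistic at 2.211 + 1.282 = 3.493. Let Φ₂ be the bivariate normal distribution function with correlation 0.5.
- Single-step (both statistics above 2.211): Φ₂(1.282, 1.282) = 0.832.
- Step-down (larger above 2.211, smaller above 1.960; 3.493 − 1.960 = 1.533): 2 × Φ₂(1.282, 1.533) − Φ₂(1.282, 1.282) = 2 × 0.860 − 0.832 = 0.888.
- Power per technique: 0.900 becomes 0.900 + 0.860 − 0.832 = 0.928.
- At least one succeeds, under either rule: 0.900 + 0.900 − 0.832 = 0.968.

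**3. Adding the pain criterion.** The pooled SD is √((19.57² + 23.33²)/2) = 21.53 and the standard error is 21.53 × √(2/131) = 2.66. The expected difference is 21.21 − 17.57 = 3.64, so the statistic has mean (17.5 − 3.64)/2.66 = 5.21 and pain power is 99.9%. Simulation with 2,000,000 draws, stepping per technique, gives:

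| Quantity | Single-step | Step-down |
|---|---|---|
| Both techniques meet both criteria | 83.0% | 88.7% |
| Power per technique | 89.9% | 92.7% |
| At least one succeeds | 96.7% | 96.7% |

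These figures are for zero correlation between pain and QoR. A correlation of 0.5 changes the first row by only a few tenths of a point. With pain power at the stated 99%, the first row is 81.7% to 82.5% against 88.0% to 88.4%.

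**4. Sensitivity to QoR power (QoR alone, both succeed).** At 80% per comparison: 69% against 77%. At 95%: 91% against 95%.

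**5. One-sided error.**
- Both techniques null on QoR: 0.025 under both rules, because any false claim needs a first rejection at the present level.
- One null, the other effective: 0.0135 becomes at most 0.025.
- One technique null on pain, the other null on QoR: about 1 − 0.9865² = 0.027 under both rules. Both technique-level claims are then false, so the step adds nothing.

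**The case against.** The strongest reply is that nothing here is wrong. The SAP applies one threshold consistently, the sample size uses the same level, and single-step testing is valid. All of that stands.

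Three stronger readings are tempting, and the document does not support them.
- **That the single-step rule buys no protection.** It does. When one technique works and the other does not, the false-claim chance for the latter is 0.0135 instead of 0.025, and the 98.65% limits are simultaneous. This is more protection than the stated family-wise aim needs, but it is real. The confidence limit is itself the pain decision, so losing simultaneity for the second technique is a genuine cost.
- **That 83% shows an underpowered trial.** The SAP promises 90% per comparison and frames its hypothesis as PVB or ICNB. It sets no target for both succeeding. The chance of at least one success does not change, and a technique gains practically nothing if the other is ineffective.
- **That stepping per technique holds the error at exactly 0.025 for the joint pain-and-QoR claim.** In the mixed case it is about 0.027, as it already is today.

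Timing also counts. The trial is open-label, and relaxing a published threshold late invites suspicion. The interim analysis described in the SAP gave the monitoring board access to TEA patients only, so a declared change made before any between-arm comparison can still be defended.

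**Conclusion.** This is a cheap improvement and not a correction of an error. The present rule is valid. A step-down form of the same correction lifts the chance that both techniques meet both criteria from about 83% to 89%: roughly one trial in nine would then miss at least one technique, against one in six. Power per technique rises from about 90% to 93%.

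The gain depends on both techniques having the design effect, on 90% QoR power, on correlation 0.5 between the two contrasts and on high pain power. The reading of the levels as Dunnett, and of the overall level as 0.05 two-sided / 0.025 one-sided, is inferred from the stated figures. No claim available under the present rule is lost.

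**What to change.** State one rule in every place that now gives the fixed level: the Methods part of the abstract, Summary of the study protocol, Analysis, Pain, Quality of recovery, and Appendix A. For example:

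*Each technique is first tested at the present levels: 98.65% one-sided limit below 17.5% in ITT and PP, and QoR p<0.027. If one technique meets both co-primary criteria, the other is tested with the 97.5% one-sided limit against the same margin in ITT and PP, and QoR p<0.05. Otherwise the present levels stand.*

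- Make the step per technique, not per outcome.
- Name the correction and the overall error level.
- Keep reporting the 98.65% limits for both techniques, and note that a 97.5% limit used for the second decision is not simultaneous.
- Leave the secondary-outcome threshold (Analysis principles and general considerations; Secondary outcomes) as it is.
- Declare the change from the published thresholds, with its date, before any between-arm comparison.

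The cost is wording and an open declaration, with no extra patients. If the sponsor prefers the simultaneous limits and the stricter protection, one sentence saying so is enough.

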#### Interim and final analysis

Since the point estimators regarding proportion of measurements with a NRS  $\geq$ 4, used in our sample size calculation for non-inferiority, were based on a small pilot study they may have limited reliability. We therefore established a Data Safety Monitoring Board (DSMB), including a methodologist, statistician and two clinical experts (anaesthesiologist and thoracic surgeon) to assess whether our study generates sufficient power to answer the research question. When 50% of the observations in the TEA group (control) were completed (n=75), the DSMB performed an interim analysis to evaluate the point estimator and variance of the proportion of NRS measurements ≥4 of the control group and advised whether adjustment of our sample size was necessary. The DSMB only had access to all patients who underwent TEA and could warn the research team of potential risk factors and suspension of inclusions. The interim analysis by the DSMB was performed in January 2023. Based on pain scores of 70 complete TEA patients (4 patients had missing data and 1 patient was treated as TEA but randomized for ICNB) in the ITT analysis, no changes in the sample size were required. The final analysis will be performed when all data of 450 patients is collected. No specific stopping rules apply since the OPtriAL has been classified as having negligible risk for study subjects. The SPIRIT flow diagram in Table 1 of the published protocol (1) demonstrates a complete overview of the schedule of assessments.

#### **Statistical principles**

The statistical analysis plan is formulated using the Guidelines for the Content of Statistical Analysis Plans in Clinical Trials and the completed checklist can be found in Appendix B. All tables and figures shown are presented with hypothetical values to help visualize the end result.

#### Analysis principles and general considerations

Continuous data will be reported as means with standard deviation (SD) or confidence intervals (CI), or medians with interquartile range (IQR) and will be compared between groups using the unpaired t-test or Mann-Whitney U, depending on the distribution of the data. Equality of variances for TEA and PVB, respectively ICNB, will be assessed with Levene's test. Categorical data will be presented as counts and percentages and data will be compared using Mantel-Haenszel Chi-squared test. In case of zero cell counts and when pooling of categories is not opportune, the Fisher's exact test will be used (7,8). For all secondary outcome measures, the CI and/or p-values will be provided to express the level of statistical significance per outcome without additional correction for multiplicity (also p<0.027). An overview of the planned statistical tests per outcome measure for group comparisons can be found in the Supplemental material (Appendix A).

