#### Protocol violation, adherence and deviation

Protocol violation is defined as non-adherence to the eligibility criteria, randomization process and study procedures, dictating that all patients should participate voluntarily and undergo an anatomical lung resection by VATS and one of the analgesic techniques (TEA, PVB or ICNB).

Protocol adherence defines that control patients should proceed to PVB catheter placement in case TEA catheter placement was unsuccessful; in case PVB too was unsuccessful, then ICNB should be done. Participants receiving TEA or PVB should have a provisional stop of the continuous analgesia at POD 2 and patients receiving TEA should have opioids administered through the epidural continuous mixture. Accidental luxation of the TEA or PVB catheter after surgery will not be seen as nonadherence.

Although the use of ERATS guidelines for enhanced postoperative recovery were advised by the protocol, it is expected that the level of implementation of each aspect of ERATS differs per hospital, for example the strict use of dexamethasone and 5-HT3 receptor antagonists. In addition, the availability of specific local anaesthetics (e.g. bupivacaine or ropivacaine) may vary and induce small between-hospital differences. To ensure equal distribution of small differences in ERATS aspects, we used treatment centre as stratification factor. Incomplete primary or secondary endpoints are considered a protocol deviation and are handled as missing data.

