#### Pain scores during rest and mobilisation

Pain scores in rest and during mobilisation will be registered at: baseline (pre-operatively); at the recovery room and in the evening of POD 0; in the morning, afternoon, and evening of POD 1-3 and at the follow-up appointment, generating 13 moments in which the pain scores are prospectively measured. Since pain scores are repeated measurements from the same patient, they are likely to be correlated and we cannot assume independency. As we expect the effect of analgesia is patient-specific and will therefore vary substantially from patient to patient, a linear mixed model will be used (Figure 3a). This analysis will lead to a more precise estimate of the trend in pain scores and how this outcome changes over time per analgesic technique. The model will include random intercepts, and baseline scores, time of the measurement and treatment group as fixed effects. The

linear mixed model will accommodate unbalanced data patterns by assuming missing data at random and use all available observations and patients in the analysis (10). We will apply the covariance matrix that fits best according to Akaike's Information Criterion (AIC) (11).

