#### QoR-15

The QoR-15 score ranges from 0-150 and will be expressed as a discrete outcome. Repeated measurements of QoR measured by the QoR-15 questionnaire taken at baseline (preoperative), from POD 0 until POD 3 and at follow-up will be analysed by a linear mixed model to depict the trend over time between the different analgesic techniques (Figure 3b).

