# Appendix A. Overview statistical test per outcome

Outcome	Planned statistical test to compare
	randomization groups (each intervention versus
	control)
Baseline characteristics	None*
Primary outcome	
% NRS ≥ 4 POD 0-2 (at rest)	Non-inferiority, upper limit 98.6% CI <17.5%
Mean QoR-15 POD 1-2	Unpaired t-test or Mann-Whitney U-test
Secondary outcomes	
% NRS $\geq$ 4 POD 0-2 (mobilization)	Unpaired t-test or Mann-Whitney U-test
% NRS $\geq$ 4 baseline, POD 0-3 and follow-up (at rest)	Linear mixed model
% NRS $\geq$ 4 baseline, POD 0-3 and follow-up	Linear mixed model
(mobilization)	
QoR-15 at baseline, POD 0-3 and follow-up	Linear mixed model
Cumulative use of analgesics POD 0-3	Unpaired t-test or Mann-Whitney U-test
Cumulative use of opioids POD 0-3	Unpaired t-test or Mann-Whitney U-test
Cumulative use of analgesics (including opioids) at follow-up	Unpaired t-test or Mann-Whitney U-test
Postoperative complications	Mantel-Haenszel chi-squared test or Fisher's
	exact test
Length of hospitalization	Mann-Whitney U-test
Patient satisfaction	Mantel-Haenszel chi-squared test or Fisher's
	exact test
Presence of chest drain	Unpaired t-test or Mann-Whitney U-test
Presence of urinary catheter	Unpaired t-test or Mann-Whitney U-test
Degree of mobility	Mantel-Haenszel chi-squared test or Fisher's exact test

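### The confirmatory QoR-15 test is left open between a t-test and Mann-Whitney although superiority is defined on the mean, and the SAP conflicts on whether an adjusted estimate decides

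*SAP*

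**What the plan says.** **Definition of success.** The SAP's Summary of the study protocol states: "Superiority regarding QoR is defined as a significantly higher mean score during POD 1 and POD 2", at p<0.027 in the ITT analysis. The section Quality of recovery repeats it: "Superiority in terms of QoR is defined as a statistically significant higher mean score".

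**Test.** Under Analysis principles and general considerations, continuous data are "compared between groups using the unpaired t-test or Mann-Whitney U, depending on the distribution of the data". The Appendix A row for mean QoR-15 on POD 1-2 reads "Unpaired t-test or Mann-Whitney U-test". Levene's test is planned for TEA against each new technique. No normality criterion, threshold or default test is given.

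**Adjustment.** The tests in Appendix A are unadjusted. Patient replacement and missing data says that imbalances read from SMDs and judged clinically will be adjusted for in a primary complete-case analysis when less than 5% of patients lack outcome data, and carries the same procedure to 5% or more. Additional analyses plans a regression of both co-primary outcomes for SMDs above 25%, with adjusted contrasts reported only where thought suitable.

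**Centre and baseline.** The Summary says "randomization is stratified by treatment centre", and the section on protocol violation, adherence and deviation adds that "it is expected that the level of implementation of each aspect of ERATS differs per hospital". Centre then enters only exploratory per-centre analyses. For the secondary pain model, "The model will include random intercepts, and baseline scores, time of the measurement and treatment group as fixed effects". Baseline QoR-15 is collected before surgery and appears only in the secondary QoR mixed model.

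**The concern.** Three things are unsettled for a confirmatory outcome.

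1. Superiority is a statement about means, but one of the two permitted tests does not address means. If Mann-Whitney is used, a significant result need not mean a higher mean score, and the stated definition is not what was tested.
2. Three sections give three positions on adjustment. If the adjusted and unadjusted results fall on different sides of 0.027, the SAP does not say which one counts.
3. The confirmatory QoR comparison leaves out the stratification factor and the baseline score, although both are available.

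The trial is unblinded, so a test and a covariate set chosen after the data are inspected are harder to defend. Pain is not affected by the first issue, because it is decided by a confidence limit for a difference in means. The second touches both co-primary outcomes.

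**Working it through.** **Inputs from the SAP.** 150 per arm, 12.6% drop-out, two-sided 0.027 per QoR comparison, stated power 90%. Pilot pain SDs are 19.57 and 23.33. The SAP gives no QoR difference, SD, distribution shape, centre variance share or baseline correlation, so 450 cannot be reproduced from it for QoR. All results below are illustrations.

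**Step 1, implied effect.** Evaluable n = 150 × (1 − 0.126) = 131 per arm. With z(1 − 0.0135) = 2.2115 and z(0.90) = 1.2816, the standardised effect giving 90% power is d = (2.2115 + 1.2816) × √(2/131) = 0.432.

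**Step 2, effect of the open choice on false positives.** Equal means and SDs, skewness 0 to 1.0:
- Choosing by distribution (assumed rule: Mann-Whitney if Shapiro-Wilk is significant at 0.05 in either arm, otherwise a Levene-guided t-test): about 2.7-3.0%.
- Taking whichever test is significant, a worst case that the SAP's rule does not permit: about 3.3-3.4%.

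**Step 3, Mann-Whitney when the means are equal.** Scores were simulated as 115 minus SD times a standardised gamma (normal at skewness 0), with SD 18 in one arm and 18 × ratio in the other, 20,000 runs per cell, Monte Carlo error about 0.1 point. Rejection rates against nominal 2.7%:

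| SD ratio | skewness 0 | 0.5 | 1.0 |
|---|---|---|---|
| 1.00 | 2.8% | 2.6% | 2.6% |
| 1.10 | 2.6% | 2.7% | 3.0% |
| 1.19 | 2.5% | 3.0% | 4.0% |

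The ratio 1.19 is 23.33/19.57, the pilot SDs for pain, borrowed for QoR. At ratio 1.19 and skewness 1.0, false superiority of the new technique (nominal 1.35%) is 3.5% if its arm is the more variable and 0.5% if TEA is. The Welch t-test stays at 2.5-2.9%.

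**Step 4, disagreement between the tests.** Equal SDs, skewness 0 / 0.5 / 1.0: different verdicts in 3.4 / 3.6 / 4.9% of trials at d = 0.432, and in 5.8 / 7.0 / 10.5% at d = 0.216.

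**Step 5, centre and baseline.** Closed forms:
- Size of the unadjusted test = 2 × (1 − Φ(2.2115/√(1 − ICC))), with ICC the share of variance due to centre: 2.33% at 0.05 and 1.97% at 0.10.
- Adjusted power = Φ(3.4931/√(1 − R²) − 2.2115): 92.7% at R² = 0.09 (centre 5% plus baseline 4%) and 96.6% at R² = 0.25 (10% plus 15%).

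The closed-form power is an upper guide. Simulated results with 12 unequal centres:

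| Assumed shares | Size, unadjusted | Size, adjusted | Power, unadjusted | Power, adjusted |
|---|---|---|---|---|
| 5% + 4% | 2.47% | 2.5% | 90.6% | 91.7% |
| 10% + 15% | 2.21% | 2.7% | 90.9% | 95.5% |

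The adjusted model pooled centres with fewer than 15 patients, filled 5% missing baseline scores by mean plus indicator, and used HC3 standard errors with error skewness 1.

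**Step 6, adjustment text side by side.** Unadjusted tests (Appendix A), a clinically judged adjustment inside a primary analysis (missing-data section) and a supplementary regression at SMD above 25% (Additional analyses) cannot all define the deciding estimate, and no sentence ranks them. Tables 1 and S1 as extracted list neither centre nor baseline QoR-15, so the SMD route would not bring either in.

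**The case against.** The strongest reply is that little is at risk. The SAP chooses by distribution, not by p-value, and such a rule holds the error close to nominal at equal SDs. This stands: a reader might infer that the open choice inflates type I error, but the SAP does not support that as a general claim. Larger Mann-Whitney figures can be produced (9.7% at an SD ratio of 1.57 and skewness 1.0), but that ratio is extreme and has no source for QoR.

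An unadjusted comparison after stratified randomisation is also valid. This stands as well: leaving out centre and baseline does not inflate type I error. It makes the test slightly conservative, and the gain from adjusting depends on shares the SAP does not give.

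Nor is the SAP silent on adjustment, or unaware of centre and baseline. A reader might infer either, but it addresses adjustment in several places, which conflict, and it uses centre in exploratory analyses and baseline in secondary models. The two adjustment rules also share a starting point, since both read imbalance from SMDs.

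The reply does not answer two points: the success criterion is a mean while a permitted test is not about means, and no sentence says which estimate decides.

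**Conclusion.** The point holds on the text, as an unfixed test and an unfixed deciding estimate. It is not a finding of demonstrated error inflation. The first two parts need no simulation. The third, centre and baseline, is a worthwhile improvement in precision and not an error.

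The practical size is modest. Under the assumptions shown, the choice of test changes the superiority verdict in about 3-5% of trials at the effect giving 90% power and in 6-11% at half that effect. Mann-Whitney departs clearly from nominal only if SDs differ and scores are skewed together (about 4% at ratio 1.19 and skewness 1). Adjustment would raise QoR power from about 90.6-90.9% to 91.7-95.5%. Different QoR SDs, shapes or correlations would change these figures. The plan should be amended before data are seen by arm.

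**What to change.** - **Quality of recovery and Appendix A:** name one confirmatory analysis, a linear model of mean POD 1-2 QoR-15 on arm, centre and baseline QoR-15 with robust (unequal-variance) standard errors. Report the adjusted mean difference with a 97.3% CI (1 − 0.027) and test at 0.027.
- **Sensitivity analyses:** keep the unadjusted Welch t-test and Mann-Whitney in this role only. State that neither Levene's test nor the observed distribution selects the confirmatory test.
- **Patient replacement and missing data, and Additional analyses:** state that imbalance-triggered adjustment is supportive and does not replace the primary estimate, for both co-primary outcomes.
- **Before data are seen by arm:** fix how small centres are pooled and one rule for missing baseline QoR-15, for example overall mean plus a missing indicator. State that the no-imputation sentence under Baseline characteristics covers the descriptive tables only.
- **Optional:** a matching model for pain, which has little to gain at a stated power of 99%.

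The minimum is one sentence naming a mean-based test and one naming the deciding estimate. The cost is SAP wording and slightly more analysis work; the data are already being collected.
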